5.3. Secondary analyses

ANCOVA (and sensitivity analyses) described above will be repeated at each of the time-points illustrated in Figure 1 (weeks 0, 6, 12, 36), using the PHQ-A, and using the GAD-A as an outcome, controlling for baseline scores. Outcomes at 6-months follow-up (pooled for both groups) will be compared to outcomes at the baseline assessment, using paired-samples t-tests (or an appropriate non-parametric test depending on the distribution of the data).

These analyses will be repeated at each of the post-intervention time-points illustrated in Figure 1 (weeks 6, 36), using the WEMWBS sub-domain scores. These between and within-group comparisons will also be summarised using effect sizes (Cohen's d).

Post-intervention measures (weeks 6, 36) will be compared to baseline measures (week 0) within each group, using paired-samples t-tests or an appropriate non-parametric test depending on the distribution of the data. Within-sample pre-post treatment effect sizes will also be computed using the method proposed by Minami et al. (2008).

We will carry out an exploratory analysis of knowledge and levels of activity before and after the intervention.

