Interventions	A 6-week, psychoeducation and physical education course consisting of online live psychoeducation sessions and physical activity sessions	
Randomization and data collection	Consenting participants will be randomly assigned to two groups; 1 and 2. Participants in both groups will be asked to complete outcome measures at an initial baseline assessment, after which only participants in group 1 will access a 6-week intervention (controlled phase). Next, group 2 will access the intervention during a 6-week period (full implementation phase). Finally, we will collect further outcome measures 6 months after both groups have completed the intervention (follow-up phase).	
Planned Sample Size	Minimum recruitment target of 192 participants, expecting 30% attrition.	
Data analysis method	 Trial data will be summarised using a CONSORT diagram and analyses will be based on intention-to-treat principles. The primary analysis will compare between and within-group differences in PHQ-A at baseline and 6 weeks, using ANOVA. Secondary analyses: between and within-group analyses will be conducted for GAD-7 and the physical activity measure at baseline and 6 weeks using ANOVA. Between-group and within-group effect sizes will be calculated using Cohen's d. Completion / dropout rates will be compared between groups using chi-square analysis. 	
Study Period	18 months (12 months active study period, plus 6 months analyses and dissemination)	

2. Background and rationale

Mental health problems cause huge public health burden in adolescents globally, as evidenced by a 20% prevalence (Belfer, 2008; World Health Organization (WHO), 2005). In the UK, the demand for Child and Adolescent Mental Health Services (CAMHS) services is at an all-time high and recent research shows children and young people referrals have increased by 26% in five years (Crenna-Jennigs & Hutchinson, 2018). Furthermore, 50% of children and young people that are assessed, wait more than 18 weeks to start treatment and over 3% wait over 12 months (Crenna-Jennings & Hutchinson, 2018).

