3.3. Hypotheses

- A) Exposure to the intervention will be associated with significantly lower mean score of depression and anxiety by comparison to a waitlist (delayed intervention) control group
- **B)** After the control group is exposed to the intervention, there will be no significant differences in mean depression and anxiety level between the two groups (immediate intervention group, delayed intervention group)
- C) Mean depression and anxiety severity for all participants at the end of the 6-month follow-up period will be significantly lower than baseline severity (prior to intervention), but not significantly different to end-of-treatment severity, indicating maintenance of gains
- **D)** Attitude towards physical exercise will significantly improve following the intervention, and be maintained at the 6-month follow-up period.

4. Study design

This will be a pragmatic, stepped wedge, open-label, randomised controlled trial. Consenting participants will be randomly assigned to two groups, by a research assistant using a computerized randomization algorithm (applying a simple 1:1 randomization schedule). Participants will take part in one of the two 6-week interventions, depending on their group assignment. They will complete an online survey with standardised measures at baseline (prior to starting the interventions), after 6 weeks (after group 1 has finished and prior to group 2 commencing), after 12 weeks (post-treatment) and finally after 6 months (follow-up). All measures will be completed online using an industry-standard survey system which automatically sends email reminders to consenting participants.

The interventions will be delivered using an online approach; weekly online video-conference sessions involving half an hour of psychoeducation and half an hour of physical activity. Both interventions will involve a total of six 1-hour sessions delivered once per week using video-conferencing software that can involve large groups of participants. The study will be carried out in four phases, which are illustrated in Figure 1.

[figure not shown]

Figure 1. Trial design and measurement time-points

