5.4. Exploratory analyses of mechanisms of change

Change scores will be computed denoting changes in theoretical mechanisms measured using the questionnaires listed in pg. 7. These change scores will be computed between time-point 0 and time-points 6, and 12, denoting changes within the intervention phase.

Residualized change scores across multiple theoretical mechanisms will be entered into a Bayesian network analysis carried out separately for each intervention group, using the post-treatment (weeks 6, 12) PHQ-A as the dependent variable. Each Bayesian network will be trained using a Tree-Augmented Naïve Bayes (TAN) algorithm with adjustment for small cell counts (Friedman, Geiger, & Goldszmidt, 1997). This method offers a data-driven way to model a network of relationships (called attribute dependencies) between predictors and their joint influence over a target outcome (post-

treatment OLBI). TAN produces a simple and parsimonious network model where each predictor is allowed to depend on one additional predictor, thus modelling multiple two-way interactions. Variable selection will be performed using a 10-fold cross-validation procedure (Rodriguez, Perez, & Lozano, 2010). The resulting treatment-specific network models will be visualised using directed acyclic graphs (Shrier & Platt, 2008), which enable an intuitive interpretation of key mechanisms of change, their relative importance, and their interrelationships.

6. Ethical considerations

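### Section 5.3 treats week 6 as post-intervention in both groups, although group 2 is still untreated then and its end-of-treatment point, week 12, is not in the list

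*Protocol*

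**What the plan says.** The within-group rule in Section 5.3 reads: "Post-intervention measures (weeks 6, 36) will be compared to baseline measures (week 0) within each group, using paired-samples t-tests". A non-parametric test is the stated alternative, and pre-post treatment effect sizes follow in the next sentence. The preceding paragraph of Section 5.3 names the same two weeks as the post-intervention time-points for the WEMWBS sub-domain scores.

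The design text puts group 2's treatment later. The Synopsis says that only group 1 receives the course in the controlled phase, and continues: "Next, group 2 will access the intervention during a 6-week period (full implementation phase". Section 4 places the surveys "after 6 weeks (after group 1 has finished and prior to group 2 commencing), after 12 weeks (post-treatment"), with a 6-month follow-up after that. Hypothesis A in Section 3.3 describes the comparison group as a waitlist with delayed intervention.

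Two neighbouring statements bear on the same point. Section 5.4 says: "These change scores will be computed between time-point 0 and time-points 6, and 12, denoting changes within the intervention phase". The first paragraph of Section 5.3 says that the ANCOVA, adjusted for baseline scores, "will be repeated at each of the time-points illustrated in Figure 1 (weeks 0, 6, 12, 36").

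**The concern.** A within-group change can be called a pre-post treatment effect only if treatment took place between the two measurements. For group 2 none takes place between week 0 and week 6. That interval is its control period, and it is the reason the arm exists.

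Two things are at stake. First, natural improvement or regression to the mean in untreated adolescents would be tabulated as an effect of the course, beside a real pre-post effect from group 1. Second, the list gives no within-group result for group 2 at the end of its own treatment, although the week-12 survey is planned for both groups.

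**Working it through.** The protocol gives no figure to reproduce here. The check sets the treatment windows against the listed contrasts, and an illustration of size follows.

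**Inputs from the protocol.** Group 1 is treated in weeks 0 to 6 (Synopsis, Section 4). Group 2 is treated in weeks 6 to 12 (Synopsis, Section 4). There are six weekly sessions (Sections 4 and 4.2), allocation is 1:1 (Section 4), and 67 per group are needed for analysis (Section 5.1).

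**Step 1: map the rule onto the design.** Two weeks in two groups give four contrasts.

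| Contrast | Sessions offered in the interval | What it measures |
|---|---|---|
| Group 1, week 0 to 6 | 6 of 6 | Pre-post change at end of treatment |
| Group 2, week 0 to 6 | 0 of 6 | Waiting-list change |
| Group 1, week 0 to 36 | 6 of 6 | Change to follow-up |
| Group 2, week 0 to 36 | 6 of 6 | Change to follow-up, including the wait |

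So 1 of the 2 week-6 contrasts, or 1 of all 4, contains no treatment. The contrast that would show group 2 at the end of treatment (week 12) is not listed.

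**Step 2: can the list be read by arm?** A reading of week 6 for group 1 and week 12 for group 2 would need week 12 in the list, and it is not there. The same pair of weeks, 6 and 36, is given twice in Section 5.3. Section 5.4, by contrast, uses weeks 6 and 12 as post-treatment. The two sections therefore disagree. The survey timing is stated in words in Section 4, so the conclusion does not depend on Figure 1.

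**Step 3: size of the mislabelled effect (assumed values).** Let w be the improvement over six untreated weeks, in SD units, and d the controlled effect. Group 1's change from week 0 to 6 is w + d; group 2's is w. With d = 0.5, taken as a moderate effect, and w from 0 to 0.3:

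- group 1: 0 + 0.5 = 0.5, up to 0.3 + 0.5 = 0.8;
- group 2: 0 to 0.3, reported under the same label.

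**Step 4: how often the mislabelled test would be significant.** For a paired t-test with n = 67, pre-post correlation r and equal SDs, the SD of the change is √(2(1 − r)) and the non-centrality is w√67 / √(2(1 − r)). For w = 0.2:

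- r = 0.5: 0.2 × 8.185 / 1.000 = 1.64, which gives 36%;
- r = 0.7: 0.2 × 8.185 / 0.775 = 2.11, which gives 55%.

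Over the same range of r, w = 0.1 gives 13% to 18% and w = 0.3 gives 68% to 88%.

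**Step 5: ANCOVA at week 0.** With the week-0 score as both outcome and covariate, the fit is exact: slope 1, group coefficient 0, residual variance 0. No group test exists.

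**The case against.** The strongest reply is that the defect is narrow and that several wider conclusions do not follow. Most of that reply stands.

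- **Half of all pre-post effects.** A reader might infer this. It is true only of the week-6 contrasts. Both week-36 contrasts follow treatment, so the share of the listed contrasts is one quarter.
- **Group 2's treatment effect is never estimated.** This goes too far. Its contrast from week 0 to 36 follows treatment, and Section 5.4 uses change to week 12 and the week-12 PHQ-A. What is missing is the week-12 result in the within-group list of Section 5.3.
- **Hypothesis C rests on these contrasts.** It does not. The baseline part has its own pooled comparison with 6 months in Section 5.3. The maintenance part compares follow-up with end of treatment, and every contrast challenged here starts from week 0.
- **Section 5.4 makes the same error.** Its networks are run separately by group with weeks 6 and 12 as post-treatment, so an arm-specific reading is open. The change-score sentence is ambiguous rather than wrong.
- **Week 6 is the only correct pre-treatment score for group 2.** The documents do not dictate this. Section 4 defines baseline as week 0. Both references can be defended, but they answer different questions.
- **The week-0 ANCOVA misleads.** It returns no usable test, so it can only be an empty analysis.

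None of this repairs the label. Week 6 is called post-intervention within each group, and the design text says that group 2 has not started by then.

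**Conclusion.** The point holds in limited form. As written, Section 5.3 reports group 2's untreated change from week 0 to 6 as a pre-post treatment effect and leaves its week-12 end-of-treatment result out of the within-group list. The within-group part of the WEMWBS analysis uses the same two weeks. The size that rests on the documents alone is 0 of 6 sessions by week 6, in one arm of a 1:1 trial, affecting one of four listed contrasts. The effect sizes and rejection rates above rest on assumed drift, effect and correlation, and serve only as illustration.

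A reader might infer that the trial's main result is compromised. The documents do not support that. At week 6 the between-group ANCOVA compares treated with waiting participants, as intended, and the label on the within-group tests does not enter it. The affected analyses are secondary and uncontrolled, so this is a should-fix.

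**What to change.** In Section 5.3:

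1. Define the post-treatment point by arm: week 6 for group 1, week 12 for group 2, and week 36 as follow-up for both. Apply this to the within-group tests, the effect sizes and the WEMWBS analysis.
2. Report group 2's change from week 0 to 6 as waiting-list change.
3. State group 2's pre-treatment reference. Week 6 isolates the treatment period; week 0 includes the wait.
4. Add the contrast of week 36 with the arm-specific end of treatment, which the maintenance part of Hypothesis C needs. The interval is 36 − 6 = 30 weeks in group 1 and 36 − 12 = 24 weeks in group 2, and this should be stated.
5. Delete week 0 from the time-points of the baseline-adjusted ANCOVA.

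In Section 5.4, state that the change-score windows follow the same arm-specific weeks.

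The cost is wording only. All four surveys are already planned for both groups, and neither sample size nor data collection changes. The definitions should be settled before results by group are seen.

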4.3. Measures

Primary outcome measure

The PHQ-A is a nine-item questionnaire; each answered on a 0 to 3 Likert scale. Items cover different aspects of depression and are worded negatively. Item scores are summed to produce a total score (range: 0 to 27), where higher scores indicate greater levels of depression. Psychometric testing has indicated that this measure was valid, reliable and acceptable measure of depression in adolescent respondents (Johnson, Harris, Spitzer & Williams, 2002). Diagnostic, criterion and construct validity were found to be adequate.

Secondary measures

- Participants will be asked to provide some demographic information, including age, gender, ethnicity
- GAD-A
- Questions related to the participants level of activity pre and post-intervention.

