- We expect that those who agree to take part in the trial complete one session for each of the six consecutive weeks, depending on whether participants are allocated to Group 1 or Group 2.

Data collection and safeguarding procedures

- All participants will be asked to complete the demographic, primary and secondary measures described above at a baseline assessment time-point (week "0" depicted in Figure 1 above). Participants will then be asked to complete a short version of this electronic questionnaire at subsequent measurement time-points depicted in Figure 1.
- The measures will be collected by the research team using a secure, web-based, industry-standard data collection system. Therefore, all data collection will be in electronic form, using unique participant pseudonyms, which cannot personally identify any of the study participants. Participants will receive email reminders (sent confidentially by the research team) at the relevant measurement points (see Figure 1) prompting them to access the survey.
- The final study dataset will be stored in a secure University network drive, only accessible to members of the research team, which is located behind The University of Sheffield Firewall. This will ensure the security and adequate storage of research data, consistent with NHS and academic codes of information governance and data protection.
- All analyses will be carried out at a University site, and data will be held in a restricted-access drive. The study dataset will be held at the University for a minimum of 5 years after the conclusion of the study.

Incentives for participation

- The participants will have the experience of being trained by sports development coaches from local sports clubs when they undertake the physical activity sessions
- The participants will have access to low level psychological interventions without referral into CAMHS, or the associated waiting times
- Participants will be provided with a certificate of achievement if they attend at least four sessions
- Participants will be eligible to be included in two prize draws for Amazon shopping vouchers.

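### The synopsis plans a between-group activity comparison at week 6, but section 5.3 names only a before-and-after analysis; the passages should be reconciled on the randomised contrast

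*Protocol*

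**What the plan says.** The synopsis, under the data analysis method, lists as secondary that "between and within-group analyses will be conducted for GAD-7 and the physical activity measure at baseline and 6 weeks using ANOVA".

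Section 5.3 allots its analyses differently. The between-group ANCOVA is to be run "using the PHQ-A, and using the GAD-A as an outcome, controlling for baseline scores". A repeat set is to be run "using the WEMWBS sub-domain scores". Activity appears only in the closing sentence: "We will carry out an exploratory analysis of knowledge and levels of activity before and after the intervention". Section 4.3 describes the instrument in similar terms: "Questions related to the participants level of activity pre and post-intervention".

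Hypothesis D in section 3.3 concerns a related but different construct: "Attitude towards physical exercise will significantly improve following the intervention, and be maintained at the 6-month follow-up period". Unlike hypothesis A, it names no comparison group.

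On timing, section 4 places a survey "after 6 weeks (after group 1 has finished and prior to group 2 commencing". Section 4.4 says of week 0: "All participants will be asked to complete the demographic, primary and secondary measures described above at a baseline assessment time-point". Later surveys use an abbreviated questionnaire whose contents are not listed.

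**The concern.** One outcome has two incompatible descriptions: a secondary analysis with a randomised comparison in the synopsis, and an exploratory before-and-after look in 5.3. The difference matters because a before-and-after contrast has no protection against background change. Young people's activity can plausibly move with season, the school calendar and pandemic rules. The Protocol says the online format exists because COVID-19 stopped face-to-face sessions, and it starts promotion in March 2021.

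If the analyst follows 5.3, a gain in activity could reflect reopening or better weather, and an unfavourable season could hide a real gain. The design already supplies the remedy, since at week 6 one randomised group has finished the course and the other has not begun. There is also a point that cannot be repaired later: if the abbreviated questionnaire leaves the activity items out for group 2 at week 6, the randomised comparison is lost.

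**Working it through.** **1. The passages side by side**

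| Place | Outcome | Contrast | Status |
|---|---|---|---|
| Synopsis | Physical activity measure | Between and within groups, baseline and 6 weeks, ANOVA | Secondary |
| 5.3, first paragraph | PHQ-A, GAD-A | Between groups, ANCOVA | Secondary |
| 5.3, second paragraph | WEMWBS sub-domains | Repeat of the above, weeks 6 and 36 | Secondary |
| 5.3, third paragraph | None named | Within each group against week 0, paired test | Secondary |
| 5.3, last sentence | Knowledge, activity level | Before and after; no comparator, test or time-point | Exploratory |
| 4.3 | Activity questions | Pre and post | Not stated |

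No sentence of 5.3 assigns activity to a between-group test. If the third paragraph is taken to cover activity, it too is within-group.

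**2. What each contrast estimates**

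Let τ be the intervention effect on activity and δ the change from week 0 to week 6 that both groups would show anyway.

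- Before-after in group 1: expectation τ + δ.
- Week 6, group 1 minus group 2, given equal expected baselines by randomisation: (τ + δ) − δ = τ.

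The shared change enters the first contrast one for one and cancels in the second.

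**3. The plan's own numbers**

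The point itself rests on no stated figure, but the group size is needed for scale. Section 5.1 gives 67 per group, so 2 × 67 = 134, and 134 / (1 − 0.30) = 191.4, rounded up to 192. The stated recruitment target is reproduced.

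**4. Illustration of scale (assumed values)**

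Assume τ = 0, a shared shift s of 0.1 to 0.3 SD, a pre-post correlation r of 0.3 to 0.7, and a two-sided 5% paired t-test. None of these comes from the Protocol's account of activity. The noncentrality is s√n / √(2(1 − r)). For s = 0.2, r = 0.5 and n = 67 it is 0.2 × 8.19 / 1 = 1.64, which gives 36.5% false rejections. The full set for n = 67:

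| Shift (SD) | r = 0.3 | r = 0.5 | r = 0.7 |
|---|---|---|---|
| 0.1 | 10.5% | 12.7% | 18.1% |
| 0.2 | 27.6% | 36.5% | 54.9% |
| 0.3 | 53.4% | 67.7% | 87.8% |

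Pooling both groups (n = 134) gives 16.3% to 99.4% over the same grid, with 63.3% at s = 0.2 and r = 0.5.

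For week-6 ANCOVA with 67 per group, 4,000 simulated trials at r = 0.5 gave a rejection rate of 4.9% with a shift of 0.2 SD and 5.1% with 0.5 SD. That is the nominal level, as step 2 predicts.

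**5. Power of the randomised contrast**

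Taking the Protocol's moderate effect as d = 0.5 (assumed; 5.1 gives no number) and a two-sided test (sidedness is not stated), 67 per group gives 81.9% power by t-test without adjustment. With baseline adjustment the residual SD is √(1 − r²), and power is 85.9%, 91.6% and 98.2% for r = 0.3, 0.5 and 0.7.

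**The case against.** The best reply is that the right comparison is already planned. The synopsis names it, and nothing in the Protocol ranks section 5 above the synopsis. The sentence in 5.3 does not say that the analysis is within-group only, and measuring before and after is compatible with comparing change between groups. If the synopsis is followed, the randomised result stands beside the within-group one and the bias argument falls away. This stands: a reader might infer that 5.3 has rejected the randomised contrast, but the text does not show that. What remains is a contradiction, plus a natural reading of 5.3 that leads to the weaker analysis.

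A second reply is that the analysis of an exploratory outcome can be left to a separate SAP. That has less force, because section 5 is itself headed as the statistical analysis plan and the complaint is a conflict within the document, not an omission. Section 5.1 also lists physical activity among the measures on which an effect might be seen.

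Third, the Protocol contains no activity trend, seasonal figure or timetable of restrictions, and March 2021 dates promotion only. This also stands. The percentages above show how before-after tests behave in general; they do not measure the bias here.

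Finally, a reader might treat hypothesis D as the hypothesis that this sentence of 5.3 tests. It is not: D concerns attitude, while 5.3 and 4.3 concern level of activity. Restating D as a difference in activity would swap its construct and drop its claim of maintenance at 6 months.

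**Conclusion.** The point holds as an inconsistency with a practical consequence. The synopsis and 5.3 disagree on both the contrast and the status of the activity analysis, and following 5.3 on its natural reading would let any shared change over time pass into the activity result in full.

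It would go too far to say that the activity result is confounded. That would require 5.3 to govern, to exclude the waitlist group, and background activity to shift during the trial; the Protocol establishes none of the three. The direction of the argument needs only that some shared change is possible. Its size is unknown, and the 10.5% to 87.8% range rests wholly on the assumed shifts and correlations.

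The reach is limited to a secondary or exploratory outcome. The absence of an untreated control after week 6 comes from the waitlist design, so later activity comparisons would be uncontrolled under either passage.

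**What to change.** - **Reconcile the passages.** Carry the synopsis comparison into 5.3 as the main activity analysis: the activity measure at week 6, group 1 versus group 2, by ANCOVA adjusting for the week-0 value. Give it the same status in both places.
- **Secure the data.** State in 4.3 and 4.4 that the abbreviated questionnaire puts the activity questions to both groups at week 6.
- **Label the rest.** Report before-after activity changes, including those at weeks 12 and 36, as descriptive.
- **Keep hypothesis D's construct.** If an attitude measure is collected, test the improvement part by the same week-6 between-group contrast, and report maintenance at 6 months as uncontrolled.

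The cost is some wording, one extra ANCOVA and, if they are not already in the abbreviated form, a few questionnaire items at week 6. No additional participants or survey time-points are needed.
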